5.4 DRUG CONCENTRATION MEASUREMENTS AND PHARMACOKINETICS

5.4.1 Assessment of Pharmacokinetics

Pharmacokinetic profiles of BI 836880 in plasma will be investigated after the first and after repeated doses. Standard plasma PK parameters as listed in [Appendix 10.3](#) will be calculated.

Pharmacokinetic data may additionally be analysed using population pharmacokinetic approach. For this purpose data may also be combined with data from other trials. Modelling activities will be planned and documented separately according to internal and external guidelines and SOP.

Exploratory pharmacokinetic interim analyses can be performed as necessary for DSB decisions, but are not expected to be done more frequently than every other DSB and do require sufficient lead time to collect samples, measure BI 836880 plasma concentrations, analyse data and prepare meaningful outputs. The final exploratory interim analysis will be performed after the cohort at MTD in the dose finding phase completed the first treatment course.

For the purpose of these exploratory interim analyses, PK plasma samples obtained up to at least 24 hours after drug administration will be used. A scientifically sound subset of the PK parameters listed in [Appendix 10.2](#) will be calculated which may include C_{max} , AUC and $t_{1/2}$, if these parameters can be reliably determined from the available samples and plasma concentration time profiles. In contrast to the final PK analysis, the interim analyses will be based on planned sampling times rather than on actual times; no supplementary subject information, e.g. on adverse events or concomitant medication, will be used in these interim analyses, and the outputs will not be validated. Minor discrepancies between interim and final results may therefore occur.

[figure not shown]
5.4.2 Methods of sample collection

[figure not shown]
For the quantification of BI 836880 plasma concentrations, at least 2 mL blood will be taken from a forearm vein in an EDTA (ethylenediaminetetraacetic acid) anticoagulant blood drawing tube at time points specified in the [Flow Chart](#) and in [Appendix 10.4](#). Plasma will be divided into duplicate aliquots and stored frozen at about -70°C at the participating sites or logistics CRO until shipment on dry ice to the bioanalytical laboratory of Boehringer Ingelheim or a Boehringer Ingelheim selected and authorized CRO.

[figure not shown]
Details about sample collection, EDTA plasma preparation, required tubes, labelling of tubes, storage and shipment (frequency and addresses) will be provided in a separate laboratory manual.

After completion of the study the plasma samples may be used for further methodological investigations, e.g., for stability testing. However, only data related to the analyte will be generated by these additional investigations, and such data will be reported separately.

The study samples will be discarded no later than 3 years after the final study report has been generated.

[figure not shown]

5.6 OTHER ASSESSMENTS

5.6.1 Demographics and history

Demographics including gender, year of birth and race/ethnicity, as well as detailed oncologic disease history will be obtained, which include date of first diagnosis of malignancy, history of previous treatment lines, as well as staging and grading information.

5.7 APPROPRIATENESS OF MEASUREMENTS

Determination of MTD is based on toxicities graded according to CTCAE version 4.03 ([R12-2532](#)). The CTCAE criteria are commonly used in the assessment of AEs in cancer patients.

[REDACTED] These criteria are well established and scientifically accepted.

6. INVESTIGATIONAL PLAN

6.1 VISIT SCHEDULE

Patients must comply with all inclusion and exclusion criteria prior to the patient enters the study (see [Section 3.3](#)).

All patients should adhere to the visit schedule as specified in the [Flow Chart](#). In case a patient misses a visit within one treatment course and the patient belatedly reports to the investigator between the missed and the next scheduled visit, the delayed visit should be scheduled as soon as possible and documented with the actual date and the reason for the delayed visit. The next visit, should still take place at the time it was originally scheduled in this treatment course. Some flexibility is allowed in scheduling the visits according to the time window specified in the Flow Chart.

However, in case the day of treatment administration (visit 1 day 1 of a course) is delayed, all subsequent visits of a course will be recalculated based on the actual date of treatment of the delayed course.

During the treatment phase, after administration of BI 836880, patients are required to be hospitalized under close surveillance with access to intensive care for at least 48 hours after administration of BI 836880 to allow close monitoring for infusion-related reactions or other adverse events and availability of patients for PK visits. After good tolerability of the first two courses of BI 836880 the investigator may evaluate the risk for an infusion-related reaction and other adverse events in view of relevant comorbidities or disease related symptoms, and as a result, shorten the duration of surveillance to 8 hours for courses 3 and 4 (PK samples included) and at investigator's discretion for further cycles.

If pathological laboratory values or other issues require an additional unscheduled visit, a new eCRF page will be created for the unscheduled visit. At the unscheduled visit, it is sufficient to record only the clinical relevant labs/examinations performed.

6.2 DETAILS OF TRIAL PROCEDURES AT SELECTED VISITS

The investigations as outlined in the Flow Chart will be performed at the respective visits. A more detailed overview of collection of blood samples for PK, [REDACTED] as well as ECG assessment and BP measurements are given in [Appendix 10.4](#).

Specific details to conduct of physical examination, collection of vital signs (incl blood pressure measurement), laboratory investigations, assessment of ECG and echocardiography can be found in [section 5.3](#).

Procedure for collection of blood samples for PK, [REDACTED] are given in [section 5.4](#) and [5.5](#).

[REDACTED]

6.2.1 Screening and run-in period(s)

Screening Period

The examinations required for the screening visit may be conducted within a time interval of 21 days prior to the first study drug administration. Prior to any other study related procedure, written informed consent must be obtained from the patient.

CT/MRI images obtained prior to study participation can be used within the study as long as they are not older than 28 days at day of first treatment.

Echocardiography must be obtained within 7 days before start of treatment.

If for administrative or medical reasons, the patient is not entered within the defined screening period, it is allowed to re screen a patient. There is no maximum time period defined for re-screening. The same Pat-ID will be used for the patient throughout the re-screening as assigned during first screening.

If the patient has been determined eligible by the investigator to enter the trial (refer to [Section 3.3](#)), the investigator will assign one or more medication number(s) to the patient through the IRT system at Visit 1 ([Section 4.1.3](#)). First dose of BI 836880 will be administered at the beginning of Visit 1 at the trial site (Day 1, cycle 1).

6.2.2 Treatment period(s)

A treatment cycle is defined as 3 weeks of duration. If initiation of a subsequent cycle is delayed due to medical reasons, additional visits beyond Day 21 may be necessary and may be performed at investigator's discretion, and should be recorded in the eCRF.

Patients may continue treatment as long as they have clinical benefit (no PD, no toxicities, no new anti-cancer treatment started) and patient is willing to continue.

During cycle 1, 2 and 4 intensive PK-sampling will be conducted and patients have to be observed closely for any adverse events. Therefore patients have to come to the clinic during the first four courses every week to the clinic. Additional visits are needed at day 2 for cycles 1, 2 and 4 and at day 3 for cycle 1. In course 5 and 6 the patient is requested to come to the clinic on day 8 after administration of study drug. From cycle 7 onwards no additional visits, beside day 1 including drug administration, are requested by protocol.

For the 2 ongoing patients, minimum set of procedures is mandatory. This includes safety lab, vital signs including blood pressure, adverse events, and pregnancy test if applicable. However, other assessments as indicated in the flowchart of the protocol or single lab values can be omitted according to investigator's opinion.

6.2.3 Follow Up Period and Trial Completion

6.2.3.1 End of treatment visit (EOT)

The EOT visit will be performed after permanent discontinuation of trial medication for any reason as soon as possible but no later than 3 weeks after permanent discontinuation of the trial medication or when the investigator decided with the patient to permanently discontinue the trial medication or became aware that the trial medication had been terminated.

6.2.3.2 Residual effect period (REP)

The REP is defined in [Section 5.3.9](#) (6 weeks). The End of REP (EoR) visit should not be performed earlier than 42 days after permanent discontinuation of the trial medication. The information collected at this visit should include all new AEs that occurred after EOT and a follow-up of adverse events ongoing at EOT. Any subsequent anti-cancer therapy administered between EoT and EoR should be reported

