Safety criteria:	Incidence and intensity of adverse events graded according to the common terminology criteria for adverse events (CTCAE, version 4.03), incidence of dose limiting toxicities; laboratory parameters, vital signs, ECG	
Statistical methods:	Dose escalation guided by a Bayesian logistic regression model with over dose control	

Proprietary confidential information © 2019 Boehringer Ingelheim International GmbH or one or more of its affiliated companies

FLOW CHART

Trial Periods	Screen	Treatment courses									EOT	EoR	FU / EoFU	
Course		1, 2, 3, 4					5, 6			7 ¹⁸ ongoing				
Week		w1		w2	w3	Imaging	w1	w2	Imaging	w1				
Visit	Screen	V1		V2	V3	V4	V1	V2	V3	V1				
Day; visit window [days]	-21 to -1	d1	d2	d3; +1d (1,2)*	d8; -1/+2d	d15; -1/+2d	d18; +/-3d (2,4)*	d1	d8; -1d/ +2d	d18; +/-3d (6)*	d1	EoT (when defined)	Last admin +42d; -2/+3d until PD	every 6 weeks (+/-3d)
Informed consent / IRT call	X													
Demographics	X													
Medical history	X													
Review of in-/ exclusion criteria ¹	X													
Height	X													
Weight	X	X						X			X	X		
ECOG performance status	X	X						X			X	X		
body temperature ²	X	X			X (1,2)*			X			X	X		
Blood pressure, heart rate ³	X	X (2x)**	X	X	X	X	X (2x)	X		X (2x)	X	X		
12-lead ECG ⁴	X	X (2x)**	X (1,2)*				X (2x)			X (2x)	X			
Echocardiography ⁵	X	if clinically indicated										X		
General safety laboratory parameters ⁶	X	X		X	X	X	X	X			X	X		
Serum pregnancy test ⁷	X	X					X				X	X		
Concomitant therapy	X	X	X	X	X	X	X	X			X	X	X	
Physical examination ⁸	X	X	X	X	X	X	X	X			X	X	X	
Adverse events ⁹	X	X	X	X	X	X	X	X			X	X	X	
Eligibility for treatment / IRT call ¹⁰	X						X				X			
Administration of BI 836880 ¹¹		X					X				X			
Pharmacokinetics ¹³			X	X	X	X (1,2,4)*	X (1,2,4)*		X		X (7-12)*	X	X (FU1)*	

Trial Protocol

Proprietary confidential information © 2019 Boehringer Ingelheim International GmbH or one or more of its affiliated companies

Trial Periods	Screen	Treatment courses									EOT	EoR	FU / EoFU	
Course *		1, 2, 3, 4									7 ¹⁸ ongoing			
Week		w1									w1			
Visit	Screen	V1									V1			
Day; visit window [days]	-21 to -1	d1	d2	d3; +1d (1,2)*	d8; -1/+2d	d15; -1/+2d	d18; +/-3d (2,4)	d1	d8; -1/+2d	d18; +/-3d (6)	d1	EoT (when defined)	EoT +42d; -2/+3d	every 6 weeks (+/-3d) until PD
Reason for treatment discontinuation												X		
Patients status												X	X	
Next line of anti-cancer therapy												X	X	

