5.3.9 Adverse event collection and reporting

AE Collection

The following must be collected and documented on the appropriate / eCRF by the Investigator:

- From signing the informed consent onwards until the end of the REP all AEs (non-serious and serious), and AESIs.
- After the end of the REP until trial completion, all related SAEs and related AESIs.
- If in an individual patient only vital status information is collected from a certain time point on, no further AEs or AESIs will be reported for this patient.

The REP is defined as 42 days (6 weeks) after the last trial medication application. All AEs which occurred through the treatment phase and throughout the REP will be considered as on treatment please see [section 7.3.4](#). Events which occurred after the REP will be considered as post treatment events.

After the last per protocol contact the Investigator does not need to actively monitor patients for AEs. However, if the Investigator becomes aware of SAEs or AESIs that occurred after the last per protocol contact, the SAEs and AESIs should be reported by the Investigator to the Sponsor if considered relevant by the Investigator.

AE reporting to sponsor and timelines

The Investigator must report SAEs, AESIs, and non-serious AEs which are relevant for the reported SAE or AESI, on the BI SAE form via fax immediately (within 24 hours) to the Sponsor's unique entry point (country specific contact details will be provided in the ISF). In specific occasions the Investigator could inform the Sponsor upfront via telephone. This does not replace the requirement to complete and fax the BI SAE form.

With receipt of any further information to these events, a follow-up SAE form has to be provided. For follow-up information the same rules and timeline apply as for initial information.

Information required

For each AE, the Investigator should provide the information requested on the appropriate (e)CRF pages and the BI SAE form, e.g. onset, end date, intensity, treatment required, outcome, seriousness, and action taken with the investigational drug(s). The Investigator should determine the causal relationship to the trial medication.

The following should also be recorded as an (S)AE in the (e)CRF and SAE form (if applicable):

- Worsening of the underlying disease (if not recorded as study endpoint, see exemption below) or of other pre-existing conditions

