7.3.4 Safety analyses

All patients of the treated set will be included in the safety analyses. Two analyses will be performed. The first analysis of safety will be performed for the first part of the trial

(determination of the MTD, first cycle only, treatment regimen = initial dose at the start of the treatment, treated set). This descriptive analysis will evaluate the MTD for the monotherapy of BI 836880. The second analysis will be performed with respect to all cycles and will act as a support for the determination of the MTD (treated set).

Events that started between the first administration of the treatment until 6 weeks (42 days) after the last administration of treatment will be considered as having occurred on treatment. In general, later events will be attributed to the post-study period and will be presented separately. However, post-study events will be examined to determine whether they need to be combined with on-treatment events in an additional table.

Adverse events will be graded according to CTCAE Version 4.03 ([R12-2532](#)) and reported according to BI standards. *Frequency, severity, and causal relationship of adverse events will be tabulated by system organ class and preferred term after coding according to the current version of the Medical Dictionary for Drug Regulatory Activities (MedDRA).*

Serious adverse events will be tabulated. In addition, events leading to dose reduction or treatment discontinuation will be examined, but may not be reported as individual tables, depending upon the extent of overlap. Descriptive statistics will be used to describe changes in laboratory tests over time. In addition, all abnormalities of potential clinical significance will be reported. In general, potential clinical significance is defined as at least CTCAE Grade 2 and an increase in CTCAE classification from baseline. The incidence and intensity of the more important adverse events (as determined from the analyses above) will be correlated descriptively with pharmacokinetic data, if possible.

Adverse events will be coded using the Medical Dictionary for Regulatory Activities (MedDRA) coding dictionary. Standard BI summary tables and listings will be produced. All adverse events with an onset between start of treatment and end of the residual effect period (REP), a period of 42 days after the last dose of trial medication, will be assigned to the treatment period for evaluation.

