6. GENERAL ANALYSIS DEFINITIONS

6.1 TREATMENT(S)

The starting dose of the study is BI 836880 40mg every three weeks, and dose escalation decision will be made by Data Safety Board (DSB).

The following treatment period will be defined:

- Screening: from the date of informed consent to the date of first study medication intake -1 day.
- On-treatment: from the date of first infusion of study drug to the date of last study drug administration + 42 days, i.e., actual on-treatment period + residual effect period (REP).
- Post-study: from the last day of on-treatment period + 1 day onwards

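### The end-of-REP (EoR) visit is dated inconsistently, and the flow chart lets it fall up to 2 days before the 42-day on-treatment period ends

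*Protocol*

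**What the plan says.** The protocol times the EoR visit in three places.

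- **Flow Chart, first page:** "Last admin +42d; -2/+3d until PD". The closing words of that cell probably belong to the neighbouring follow-up column, where the continuation page has them; nothing here depends on them.
- **Flow Chart, continuation page:** the same visit and the same -2/+3 day window, but counted from the EoT visit.
- **Section 6.2.3.2:** "The End of REP (EoR) visit should not be performed earlier than 42 days after permanent discontinuation of the trial medication".

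The period that this visit is meant to close is defined consistently. Section 5.3.9: "The REP is defined as 42 days (6 weeks) after the last trial medication application". Section 7.3.4 treats as on treatment "Events that started between the first administration of the treatment until 6 weeks (42 days) after the last administration of treatment". SAP section 6.1 runs the on-treatment period "from the date of first infusion of study drug to the date of last study drug administration + 42 days".

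Section 5.3.9 also sets what is collected. Up to that point: "From signing the informed consent onwards until the end of the REP all AEs (non-serious and serious), and AESIs". Beyond it: "After the end of the REP until trial completion, all related SAEs and related AESIs".

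Section 6.2.3.1 places EoT as soon as possible and "no later than 3 weeks after permanent discontinuation of the trial medication". It then adds, as alternatives, the time at which stopping was decided or at which the investigator learned of it. Section 6.2.3.1 does not say whether permanent discontinuation is the day of the last dose or the day of the decision, and nor does 6.2.3.2. Under 6.2.3.2, EoR is to gather the adverse events that are new since EoT.

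**The concern.** A site cannot satisfy all three statements about EoR. One that follows the first flow chart page exactly may hold the visit on day 40 or 41 after the last dose, while the REP and the on-treatment period run to day 42.

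What is at stake is completeness of adverse-event ascertainment at the end of the on-treatment period. After EoR, section 6.2.3.3.1 schedules further visits only for patients who have not progressed. Progression is itself a reason to stop treatment (section 3.3.4.1, with an exception for intra-patient escalation). For a progressed patient EoR can therefore be the last planned contact, and section 5.3.9 does not require active monitoring after that contact. An event that starts on day 41 or 42 counts as on treatment, but no one is scheduled to ask about it.

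A second problem depends on a reading that the protocol leaves open. If the EoT limit runs from the decision date, EoT and the first-page EoR can fall together or in reverse order. EoR could then not do its stated job of collecting what is new since EoT.

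**Working it through.** Calendar arithmetic, with day 0 = last administration.

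**Inputs**
- REP: 6 weeks from last application (5.3.9).
- EoR windows: Flow Chart, both pages; section 6.2.3.2.
- EoT limit: 3 weeks (6.2.3.1).
- Dosing interval: 3 weeks (3.1).
- Re-evaluation before a decision on further treatment: up to 2 weeks (4.1.4).

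**The plan's own figure.** 6 × 7 = 42 days, as stated. The REP and the on-treatment period end on day 42.

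**First-page window against the REP**
- Earliest EoR: 42 − 2 = day 40. Latest: 42 + 3 = day 45.
- Visit on day 40: 42 − 40 = 2 REP days follow it (days 41 and 42).
- Visit on day 41: 42 − 41 = 1 REP day follows it.
- Largest share of the REP: 2/42 = 4.8%.
- Visit on days 42 to 45: none.

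**The three timings under each reading.** Let D be the day of permanent discontinuation. EoT then falls between D and D + 21. EoR under 6.2.3.2 is D + 42 or later. EoR on the continuation page falls between D + 40 (EoT on D) and D + 21 + 45 (EoT at its limit).

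| D | EoT | EoR, first page | EoR, 6.2.3.2 | EoR, continuation page | EoT days inside first-page window |
|---|---|---|---|---|---|
| 0 (last dose) | 0–21 | 40–45 | ≥ 42 | 40–66 | none |
| 21 (next dose due) | 21–42 | 40–45 | ≥ 63 | 61–87 | 40–42 |
| 35 (21 + 14) | 35–56 | 40–45 | ≥ 77 | 75–101 | 40–45 |

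- **D = last dose.** The first page and 6.2.3.2 share an anchor, and the -2 days contradicts the 42-day minimum directly. The continuation page still differs. EoT is on day 21 at the latest, so it cannot meet EoR.
- **D = decision date.** There are three different dates. EoT can reach the first-page window once D + 21 ≥ 40, that is, D ≥ 19. With D = 35, EoT may fall as late as day 56, after the first-page window has closed on day 45.

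The inconsistency is present under both readings. The EoT/EoR overlap arises only under the second.

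**Check of the remedy.** With last administration as anchor and -0/+3 days, EoR is on days 42 to 45 and 42 − 42 = 0 REP days are uncovered. If 6.2.3.1 stays as it is, a decision on day 35 still allows EoT up to day 56, after EoR. Changing the EoR window alone is therefore not enough.

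**The case against.** The strongest reply is that no cut-off depends on the visit. Section 5.3.9 requires all adverse events to the end of the REP, a date fixed by the last dose, and the protocol and SAP classify events by that same date. This stands. Classification is unaffected, and an early EoR does not shorten the collection period on paper. What remains is the missing scheduled contact for days 41 and 42.

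Section 6.2.3.2 also refers back to 5.3.9 for the REP, so permanent discontinuation can fairly be read as last application. That would remove the third anchor and the overlap with EoT. It would not remove the conflict between the two flow chart pages, or between the -2 days and the 42-day minimum.

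A reader might infer more than the documents support:

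- **That EoR itself ends the recording of all adverse events.** It does not; the date does.
- **That the range of possible EoR days measures lost data.** With D = 21 the extremes are days 40 and 87, or 47 days apart. Every visit from day 42 on still covers the whole REP, so only the early allowance shortens coverage.
- **That pharmacokinetic results suffer because EoR carries a sample.** The secondary PK endpoints concern the first dose (5.1.2), and 5.4.1 implies that the final PK analysis uses actual sampling times. No affected analysis can be named.
- **That the end of the trial becomes uncertain.** Sections 6.2.3.5 and 8.6 word it differently (REP completed, EoR visit completed), but this is administrative and changes no analysis.
- **That early visits are allowed in breach of a prohibition.** Section 6.2.3.2 says that the visit should not be earlier, which is softer than a ban.

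**Conclusion.** The timing of EoR is internally inconsistent in the current protocol text, and the passages need to be reconciled. The demonstrable consequence is narrow: at most 2 of the 42 REP days (4.8%) without a scheduled contact. It applies only to patients whose EoR is held on day 40 or 41 and who have no later visit.

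This rests on the first flow chart page being followed as written. The overlap of EoT with EoR rests on the further assumption that permanent discontinuation means the decision date, taken on day 19 or later. The documents allow that reading but do not settle it.

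The practical effect from here on is small. Version 6.0 refers to 2 ongoing patients, and under section 6.2.3.5 data collected after database lock go to separate listings, with tables not updated unless deemed necessary. The documents do not say how many earlier patients had EoR on day 40 or 41, so the effect on data already collected cannot be sized here.

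**What to change.** 1. In both flow chart pages and in 6.2.3.2, date EoR from last administration, as 5.3.9, 7.3.4 and SAP 6.1 already do for the REP, with a window of +42 days, -0/+3.
2. Define permanent discontinuation as one date and use it consistently.
3. Align the EoT limit in 6.2.3.1 with that definition so that EoT always precedes EoR, and say what applies if the decision to stop comes too late for this.
4. State that EoR asks about all adverse events with onset through day 42.

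The cost is a change of wording in the flow chart and in two short sections, plus the loss of 2 days of early scheduling flexibility. The analysis definitions in the SAP need no change.
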